## MEDICAL PROTOCOL (HRP-590)

PROTOCOL TITLE: Combining cerebellar tDCS and constraint-induced language therapy in non-fluent aphasia: a novel approach to target discourse

VERSION DATE: 08/09/2023

*open-ended questions regarding barriers to participation will be analyzed to identify common themes.*

- Primary outcome measures, main concept discourse scores and verbal fluency counts, will be compared between treatment conditions using mixed effects generalized linear models, with fixed effects for treatment, period, sequence, pre-post time point, and treatment by pre-post time point interaction, and random effects for participant within sequence. This will provide difference-in-differences (post-treatment minus pre-treatment) estimates for the treatment effect which will be reported along with 95% confidence intervals as a measure of precision. Similar models will be used to analyze the secondary outcome measures including WI card sorting task, EEG delta wave, and SAQOLL.*
- Estimates from these models will provide important information for planning a well-powered clinical trial that are not obtainable elsewhere. Estimates that will be gathered in this pilot trial that will inform the subsequent power calculation include the treatment effect size, within-participant correlation of repeated measures, and random effects variance, for each of the outcome measures.*
- Pearson's Correlation will be conducted to determine the relationship between primary outcome variables (discourse and working memory scores) and SS-QOL as well as other scaled demographic variables such as age and duration since stroke.*
- Spearman's Rho Correlation analyses will be conducted to determine the relationships between primary outcome variables (discourse and working memory) and EEG data, reported in percentage.*
- The multivariate repeated measures and correlation analyses may not be terribly informative as the pilot sample size may lack the power for these statistics. However, they may be useful in descriptive interpretation of the data and lay the foundation for the larger clinical trial.*

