### 4. Study Intervention(s)/Investigational Agent(s)

#### 4.1. Description:

There will be two intervention conditions in this study:

- 1) anodal tDCS (2mA) to the right cerebellum; and
- 2) sham tDCS to the right cerebellum.

The participants will receive 20 minutes of tDCS (sham or real) during constraint-induced language therapy (CILT) followed by an additional 20 minutes of CILT alone.

tDCS (TCT Research Limited; Hong Kong): 5x5 saline-soaked sponge electrodes will be used with the anode placed over the right cerebellar hemisphere; 1cm under and 4cm lateral of the inion targeting lobule VII and the anode will be placed on the right shoulder (Ferrucci et al., 2015; Sebastian et al., 2020). The electrode placement will be the same across both conditions.

CILT: The CILT behavioral intervention will be led by a certified, licensed speech-language pathologist and a graduate student assistant and will follow the guidelines of CILT (Maher et al., 2006; Mozeiko et al., 2016; Pulvermuller et al., 2001). During the behavioral language intervention, participants will engage in language activities such as card games that require verbal expression. Other forms of communication such as gestures and writing will be discouraged and only verbal output will be encouraged through the use of cues and, when needed, models.

As this is a within subject study, all participants will experience both intervention conditions through a cross over design. Each condition will

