## MEDICAL PROTOCOL (HRP-590)

PROTOCOL TITLE: Combining cerebellar tDCS and constraint-induced language therapy in non-fluent aphasia: a novel approach to target discourse

VERSION DATE: 08/09/2023

*of 21.5 hours of participation over the course of the study. If a participant misses an intervention session, we will attempt to make it up during that same week of intervention and reschedule the assessment day. The timing of the assessment day post intervention is critical as tDCS does not appear to have long-lasting effects. The post intervention assessment visit would have to take place within 1-2 days of the last intervention day. If rescheduling is not an option, the total number of intervention sessions attended will be noted in the data. However, if 2 sessions have been missed within either of the intervention periods, the participant will need to be re-enrolled or dropped from the study. Participants will be randomly assigned to receive either the real or sham tDCS first.*

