## 10. Local Number of Participants

10.1. Local Number of Participants to be Consented: *A total of 5 participants will be enrolled with the goal of 3 participants to complete the duration of this pilot study.*

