## 15. Statistical Considerations

15.1. Data Analysis Plan:

*All data will be de-identified and entered into Excel and SPSS for analysis. Visual analysis will be conducted initially with plotting of descriptive statistics.*

15.2. Power Analysis:

*A literature review of studies measuring the impact of cerebellar tDCS in aphasia did not find usable estimates of variation (SD, SEM, IQR, etc.) for the outcomes of interest. Accordingly, using a standard effect size scale (Cohen's d, scaling the treatment effect size relative to between-participant SD), and a range of plausible within-participant correlations of +0.4 to +0.9, we estimate that enrolling 4 participants will provide 80% power to detect large ( $d=0.9$ ) to very large ( $d=2.3$ ) treatment effect sizes using a two-sided 5% significance level.*

*A post-hoc power analysis will be conducted using the information gathered in the pilot study to determine the sample size needed for a larger study.*

15.3. Statistical Analysis:

*BDAC was consulted regarding the plan for statistical analysis.*

*Based on their recommendations, the following plan was created.*

*Throughout the project, BDAC will be consulted to review this statistical analysis plan and provide additional insight to alternative statistical processes best suited for the data as needed.*

*• The quantitative data for attrition rate and adverse events will be descriptive in nature and will be reported as counts and rates. The*

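### The 15.3 model does not adjust the difference-in-differences for a period difference in gain, and the plan has no rule for when treatment and period cannot be separated

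*Combined protocol and SAP*

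**What the plan says.** Section 15.3 analyses the primary outcomes by mixed effects generalized linear models "with fixed effects for treatment, period, sequence, pre-post time point, and treatment by pre-post time point interaction", with a random effect for participant within sequence. Only treatment interacts with time point. "This will provide difference-in-differences (post-treatment minus pre-treatment) estimates for the treatment effect", reported with 95% confidence intervals. The result is then passed on: "Estimates that will be gathered in this pilot trial that will inform the subsequent power calculation include the treatment effect size". The same section warns that the repeated-measures and correlation analyses "may not be terribly informative as the pilot sample size may lack the power for these statistics", and it offers statistical consultation on alternative methods if the data call for them.

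On order, section 5.2 says only: "Participants will be randomly assigned to receive either the real or sham tDCS first". The documents give no ratio, blocking or balance rule. Standard operating procedures are mentioned in the revision history and in 15.4, but they are not among the documents. On numbers, section 10.1 says: "A total of 5 participants will be enrolled with the goal of 3 participants to complete the duration of this pilot study". Section 12.2 keeps the data collected before a withdrawal unless the participant objects. No section says what happens if all analysed participants received the conditions in the same order.

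**The concern.** A period main effect moves the pre and post scores of a period by the same amount. It corrects for a difference in level between periods but drops out of every gain, and the treatment effect here is a difference in gains. A difference in gain between periods is possible: CILT is given in both conditions (4.1), and the same discourse and fluency tasks are used at four assessments (3.1 and Table 1). Practice, or a smaller response to a second course of therapy, would produce one. The documents give no size for it.

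Equal sequences would cancel such a difference, but neither 3 completers nor 5 enrolled can split equally. In the extreme case of a single sequence, treatment and period cannot be told apart, yet the planned model still returns an estimate and an interval. That number could become the effect size on which the larger trial is planned.

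**Working it through.** **The plan's own figure (15.2).** The statement is: "we estimate that enrolling 4 participants will provide 80% power" for d = 0.9 to 2.3. A paired t-test with n = 4 (df 3) has 80% power at a standardised difference of 2.128. Multiplying by √(2(1 − ρ)) gives 2.128 × √0.2 = 0.95 at ρ = 0.9 and 2.128 × √1.2 = 2.33 at ρ = 0.4. The printed range is therefore reproduced apart from rounding, by a calculation without a period term.

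**Set-up for the check.** Linear model with participant effects, period, treatment, time point and treatment by time point, fitted with and without period by time point. Residual SD is 1. Let n1 and n2 be the completers in each sequence, n = n1 + n2, and g1, g2 the mean gains in periods 1 and 2 with no true treatment effect.

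**Leak under the planned model, complete data.** The estimate is mean real gain minus mean sham gain:

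(n1·g1 + n2·g2)/n − (n1·g2 + n2·g1)/n = (n1 − n2)/n × (g1 − g2).

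Each gain has variance 2, so the planned estimate has variance 2/n + 2/n = 4/n. With the added term, the estimate averages the two within-period contrasts. It has no leak and variance 1/n1 + 1/n2.

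| Split | Fraction leaked | Variance, planned / with term | Residual df, planned / with term | Coverage of planned 95% CI at a period difference of 1, 2, 3 SD |
|---|---|---|---|---|
| 2:2 | 0 | 1.000 / 1.000 | 8 / 7 | not simulated; no leak |
| 3:2 | 1/5 | 0.800 / 0.833 | 11 / 10 | 96, 97, 98% |
| 2:1 | 1/3 | 1.333 / 1.500 | 5 / 4 | 95, 96, 98% |
| 3:1 | 1/2 | 1.000 / 1.333 | 8 / 7 | 94, 91, 90% |
| 4:1 | 3/5 | 0.800 / 1.250 | 11 / 10 | 92, 84, 75% |
| 3:0 | all | 1.333 / not estimable | 6 / none | 89, 69, 41% |

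The period differences of 1, 2 and 3 residual SDs are assumptions. Coverage is from 100,000 simulations per cell; for 3:0 the exact values are 88.6, 69.1 and 41.5%. With the term, coverage is 95% wherever the effect is estimable. At 2:1 and 3:2 the unmodelled difference also inflates the residual variance, so the planned interval does not undercover.

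**Bias against variance at 2:1.** Root mean squared error of the planned estimate is √(1.333 + (D/3)²), which is 1.15, 1.20, 1.33 and 1.53 for D = 0, 1, 2 and 3. With the term it is √1.5 = 1.22 throughout. The curves cross at D = √(1.5 − 1.333)/(1/3), about 1.2 residual SDs.

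**One sequence among completers, with withdrawn participants' data kept (12.2).** Take three completers in one sequence, plus participants in the other sequence who have a complete period-1 gain only.

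- Plus one: the planned estimate is g1 − (3·g2 + g1)/4, a leak of 0.75. With the term, the effect is the contrast of period-1 gains, with zero leak and variance 2(1/3 + 1/1) = 2.67.
- Plus two: the planned estimate is g1 − (3·g2 + 2·g1)/5, a leak of 0.60. With the term, zero leak and variance 2(1/3 + 1/2) = 1.67.
- No such participant: the effect with the term is not estimable, and the planned estimate is treatment plus the whole period difference.

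**Chance of full aliasing with 3 completers of 5.** Simple 1:1 randomisation (assumed): 2 × 0.5³ = 25% if neither withdrawn participant has a complete period-1 gain, and 2 × 0.5⁵ = 6.25% if both do. A 3:2 list with random dropout: 1/C(5,3) = 10% if neither does. It is 0 if either does, because in that outcome both withdrawn participants are in the other sequence.

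**The case against.** The best defence is that this is a pilot whose plan already limits what may be read from the model. It reports intervals, begins with visual analysis, says the models may tell little, and offers statistical consultation. No period difference in gain is documented. The leak averages zero over randomisations. With 3 completers the only mixed split is 2:1, where the planned interval holds its level and the added term lowers mean squared error only above about 1.2 residual SDs. All of this stands, and it rules out calling the planned model wrong. The plan's caveat concerns power rather than confounding, however, and an offer of consultation is not a rule fixed in advance.

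Two stronger readings are tempting. A reader might infer that the planned estimate is systematically biased. The documents do not support that, since random order makes the expected leak zero; the issue is the split that actually occurs. A reader might also infer a 25% (or 10%) chance that no treatment effect can be estimated with 3 completers. Those figures count completers only. Section 12.2 keeps data from withdrawn participants, and one complete period-1 gain in the other sequence makes the effect estimable once the term is added. They are upper limits.

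The magnitudes come from a linear model, whereas 15.3 specifies generalized linear models and includes counts. They would not carry over exactly.

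**Conclusion.** The point holds and is minor. Period as a main effect does not adjust the difference-in-differences for a period difference in gain. The share that enters follows from the sequence split, given a linear model and complete data; the size of the period difference is unknown. Undercoverage appears at 3:1, 4:1 and one-sequence outcomes, but not at 2:1 or 3:2. Making the adjusted model primary is a choice between bias and variance, and the documents do not settle it.

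The firmer part is the missing rule. When every analysed gain comes from one sequence, the plan yields a treatment effect that cannot be separated from period. When only withdrawn participants' period-1 data supply the other sequence, the planned model still leaks 0.75 or 0.60 in the cases worked above. In either case 15.3 would pass the number to the larger trial's power calculation.

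**What to change.** 1. Keep the planned model, and also report the treatment effect with a period by pre-post time point term as a sensitivity analysis. Carry both estimates to the larger trial's power calculation. If there is no period difference, the term costs one residual degree of freedom. At 2:1 the 95% CI is √(1.5/1.333) × 2.776/2.571 = 1.146 times as wide, about 15% wider (about 18% at 3:1, 3% at 3:2, 2.5% at 2:2). At 2:1 and 3:1 the single participant in the smaller sequence then carries half of the estimate.
2. State that if the treatment by pre-post effect is not estimable with that term, using all data kept under 12.2, no treatment effect is reported from the planned model or used as the larger trial's effect size. If it is estimable only through period-1 data from withdrawn participants, report the estimate with the term and its CI, flagged as partly between-participant.
3. Allocate order from a concealed, pre-generated list balanced between the two sequences. This makes a one-sequence outcome less likely but cannot exclude it after dropout. Small blocks can make the order predictable to staff who know the device setting.

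The cost is SAP wording and a list; no participants or visits are added.

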### 15.4. Data Integrity:

*Data collection is the responsibility of the research team under the supervision of the PI. The investigator is responsible for ensuring the accuracy, completeness, legibility, and timeliness of the data reported. All research staff will have extensive training in the procedures of data collection by following the Standard Operating Procedures for the study. Behavioral data (scores on discourse tasks, Wisconsin Card Sorting, verbal fluency) will be collected on a paper data form (see supplemental*

## MEDICAL PROTOCOL (HRP-590)

PROTOCOL TITLE: Combining cerebellar tDCS and constraint-induced language therapy in non-fluent aphasia: a novel approach to target discourse

VERSION DATE: 08/09/2023

*documents), using participant code. The EEG data will be stored within MatLab, again using participant code. Data will then be entered into a de-identified excel document stored UMN Secure Box and transferred into an SPSS file when preparing for statistical analysis. The SPSS files will also be deidentified. The de-identified excel and SPSS files will be stored in UMN secure Box folder. All IRB approved research staff will have access to these files in Box. The master database of participant names and codes will be kept in a digital file in UMN secure Box folder as well. IRB approved research staff will have access to this file as well. If research staff changes, ie: graduate student completes program and is transitioned off of the research team, they will be removed from the shared folder.*

## 16. Health Information and Privacy Compliance

16.1. Select which of the following is applicable to your research:

My research does not require access to individual health information.

I am requesting that all research participants sign a HIPCO approved HIPAA

Disclosure Authorization to participate in the research (either the standalone form or the combined consent and HIPAA Authorization).

I am requesting the IRB to approve a Waiver or an alteration of research participant authorization to participate in the research.

Appropriate Use for Research:

16.2. Identify the source of Private Health Information you will be using for your research (Check all that apply)

I will use the Informatics Consulting Services (ICS) available through CTSI (also referred to as the University's Information Exchange (IE) or data shelter) to pull records for me

I will collect information directly from research participants.

I will use University services to access and retrieve records from the Bone Marrow Transplant (BMPT) database, also known as the HSCT (Hematopoietic Stem Cell Transplant) database.

I will pull records directly from EPIC.

I will retrieve record directly from axiUm / MiPACS

## MEDICAL PROTOCOL (HRP-590)

PROTOCOL TITLE: Combining cerebellar tDCS and constraint-induced language therapy in non-fluent aphasia: a novel approach to target discourse

VERSION DATE: 08/09/2023

I will receive data from the Center for Medicare/Medicaid Services

I will receive a limited data set from another institution

Other. Describe:

16.3. Explain how you will ensure that only records of patients who have agreed to have their information used for research will be reviewed.

*All participants in this study will consent and sign a HIPAA authorization. Data will be collected directly from said participants with no review of their medical records.*

16.4. Approximate number of records required for review: 5

16.5. Please describe how you will communicate with research participants during the course of this research. Check all applicable boxes

This research involves record review only. There will be no communication with research participants.

Communication with research participants will take place in the course of treatment, through MyChart, or other similar forms of communication used with patients receiving treatment.

Communication with research participants will take place outside of treatment settings. If this box is selected, please describe the type of communication and how it will be received by participants.

*We will communicate with participants via: proofpoint secure emails, telephone (using study-specific phone number), text message (if participant agrees by signing the consent for text message correspondence), unsecure email (if the participant agrees by signing the consent for unsecure email correspondence).*

16.6. Explain how the research team has legitimate access to patients/potential participants:

16.7. Location(s) of storage, sharing and analysis of research data, including any links to research data (check all that apply).

In the data shelter of the [Information Exchange \(IE\)](#)

Store       Analyze       Share

In the Bone Marrow Transplant (BMT) database, also known as the HSCT (Hematopoietic Stem Cell Transplant) Database

Store       Analyze       Share

## MEDICAL PROTOCOL (HRP-590)

PROTOCOL TITLE: Combining cerebellar tDCS and constraint-induced language therapy in non-fluent aphasia: a novel approach to target discourse

VERSION DATE: 08/09/2023

In REDCap (recap.ahc.umn.edu)

Store  Analyze  Share

In Qualtrics (qualtrics.umn.edu)

Store  Analyze  Share

In OnCore (oncore.umn.edu)

Store  Analyze  Share

In the University's Box Secure Storage (box.umn.edu)

Store  Analyze  Share

In an AHC-IS supported server. Provide folder path, location of server and IT Support Contact:

Store  Analyze  Share

In an AHC-IS supported desktop or laptop.

Provide UMN device numbers of all devices:

Store  Analyze  Share

Other:

Indicate if data will be collected, downloaded, accessed, shared or stored using a server, desktop, laptop, external drive or mobile device (including a tablet computer such as an iPad or a smartform (iPhone or Android devices) that you have not already identified in the preceding questions

I will use a server not previously listed to collect/download research data

I will use a desktop or laptop not previously listed

I will use an external hard drive or USB drive ("flash" or "thumb" drives) not previously listed

I will use a mobile device such as a tablet or smartphone not previously listed

16.8. Consultants. Vendors. Third Parties: N/A

16.9. Links to identifiable data:

*All data will be identified with an identification code unique to the participant. Study staff will keep the mapping of identification code to the*

## MEDICAL PROTOCOL (HRP-590)

PROTOCOL TITLE: Combining cerebellar tDCS and constraint-induced language therapy in non-fluent aphasia: a novel approach to target discourse

VERSION DATE: 08/09/2023

*identity of the participant on an encrypted password protected computer stored separately from the data in Box. That same identification code will be used for data-entry into Box. Any internal data reports will use only these codes and will not use any identifiable information. Any external data reports, abstracts, publications, presentations, etc. will present de-identified, grouped, and/or aggregate data. Any reports to the University of Minnesota IRB (such as Adverse Event reporting and annual renewal reports) will be kept confidential; they will not include participant-identifiable information; only the participant's identification code will be used.*

### 16.10. Sharing of Data with Research Team Members:

*Only IRB-approved members of the study team will have access to the data. Data will be shared through UMN Secure Box.*

### 16.11. Storage of Documents:

*Paper documents will be stored in a locked cabinet in a locked research office only accessible to research staff.*

### 16.12. Disposal of Documents:

*Disposal of all study documents will be in accordance with the university policy.*

## 17. Confidentiality

### 17.1. Data Security:

*All data will be securely stored in UMN Secure Box. De-identified data in the form of an excel data spreadsheet and SPSS data file will be securely stored in Box. The informed consent will NOT be placed in the participant's medical file or clinic file (if a client in the RFP Speech-Language Hearing Clinic).*

